8.6.2. Clinical Laboratory Parameters

All clinical laboratory parameters, with changes from baseline, will be listed; any value outside the clinical reference range will be flagged, and whether the out of range value was deemed clinically significant or not clinically significant will be indicated.

The observed results and change from baseline for clinical chemistry, hematology, and coagulation parameters, with changes from baseline will be summarized descriptively by hepatic function group and timepoint.

Values recorded as $< x$, $\leq x$, $> x$, or $\geq x$ will be displayed in the listings as recorded. For the derivation of listing flags, calculation of summary statistics, $< x$ and $\leq x$ values will be set to 0, whereas $> x$ and $\geq x$ values will be set to x.

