Appendix 2: Clinical Laboratory Evaluations

Clinical Chemistry Panel				
(Fasted):	Hematology Panel:	Other Tests:		
Alanine aminotransferase	Hematocrit	Hemoglobin A1c ^b		
Albumin	Hemoglobin	Thyroid-stimulating hormone ^b		
Alkaline phosphatase	Mean corpuscular	Estimated glomerular filtration rate ^{a,d}		
Amylase	hemoglobin	SARS-CoV-2 (COVID-19) test		
Aspartate aminotransferase	Mean corpuscular			
Bilirubin (direct and total)	hemoglobin concentration	Coagulation Parameters:		
Blood urea nitrogen	Mean corpuscular volume			
Calcium	Platelet count	Partial thromboplastin time Prothrombin time		
Chloride	Red blood cell (RBC) count	International normalized ratio		
Cholesterol	RBC distribution width			
Creatine kinase	White blood cell (WBC)	C I b		
Creatinine	count	Serology:b		
Glucose	WBC differential (percent	Human immunodeficiency virus		
Iron	and absolute):	antibody		
Lipase	Basophils	Hepatitis B surface antigen		
Magnesium	Eosinophils	Hepatitis B virus immunoglobulin M		
Phosphorus	Lymphocytes	core antibody ^f		
Potassium	Monocytes	Hepatitis C virus antibody (healthy		
Sodium	Neutrophils	matched-control subjects only) ^f		
Total protein		For Female Subjects only:		
Triglycerides		Pregnancy test (serum qualitative,		
Uric acid	Urinalysis:	serum quantitative may be used for		
	Bilirubin	confirmation if needed) ^c		
		Follicle-stimulating hormone		
	Color and appearance	(post-menopausal female subjects		
Urine Drug Screen: ^a	Glucose	only) ^b		
Including but not limited to the	Ketones			
following:	Leukocyte esterase Nitrite			
Alcohol (ethanol) ^e	Occult blood			
Amphetamines				
Barbiturates	pH and specific gravity Protein			
Benzodiazepines				
Cannabinoids	Urobilinogen Migragagnia ayaminatian			
Cocaine (metabolite)	Microscopic examination including bacteria, casts,			
Methadone	crystals, epithelial cells,			
Opiates	RBCs, and WBCs (if protein,			
Phencyclidine	leukocyte esterase, nitrite, or			
Cotinine (healthy subjects	blood is positive)			
only)	olood is positive)			
a Performed at Screening and Check-	: (D 1)1	•		

- a. Performed at Screening and Check-in (Day -1) only.
- b. Performed at Screening only.
- c. Performed at Screening, Check-in (Day -1), and Day 7//Early Termination (ET) only.
- d. Calculated using the using the Chronic Kidney Disease Epidemiology Collaboration (CKD-EPI) equation
- e. Urine or breath test.

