8.1.3. Definitions of Baseline and Change from Baseline

Baseline value is defined as the last non-missing measurement before administration of LOXO-305.

If the date/time of the value is incomplete or missing, it will be excluded from the baseline calculation, unless the incomplete date/time indicates the value was recorded prior to dosing.

Individual changes from baseline will be calculated by subtracting the individual subject's baseline value from the value at the timepoint. The mean change from baseline will be defined as the mean of the individual changes from baseline for all subjects.

See [Section 8.1.2](#) for more detail on handling repeat and unscheduled readings in the calculations.

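### Setting laboratory results recorded as below a limit to 0 lowers group means, widens the spread of changes from baseline and, with flags built on substituted values, allows wrong flags at both ends

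*SAP*

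**What the plan says.** SAP Section 8.6.2 handles laboratory results that carry an inequality sign. In the listings they "will be displayed in the listings as recorded". For other uses, introduced by "For the derivation of listing flags, calculation of summary statistics", the rule for results recorded as `<x` or `<=x` is that the "values will be set to 0, whereas" for `>x` and `>=x` the "values will be set to x".

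Two outputs depend on this. The first is the flag: "any value outside the clinical reference range will be flagged, and whether the out of range value was deemed clinically significant" or not is to be shown. The second is the set of tables by hepatic function group and timepoint: "The observed results and change from baseline for clinical chemistry, hematology, and coagulation parameters" are summarised descriptively. SAP Section 8.1.3 defines change: "Individual changes from baseline will be calculated by subtracting the individual subject's baseline value from the value at the timepoint". Section 8.6.2 does not name changes from baseline in the substitution sentence. Their summaries need a number, however, and no other rule is given, so I read the substitution as applying to them.

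Protocol Appendix 2 lists the analytes, among them "Bilirubin (direct and total"), but neither document gives a reporting limit, a reference range or an expected share of results outside the reporting range.

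**The concern.** A result recorded as `<x` lies somewhere between 0 and x. Replacing it by 0 takes the most extreme value possible, so every error goes in the same direction. At the upper end the rule uses the limit itself, so the two ends are treated differently.

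A subject whose value moves from just below x to just above it is credited with a change of about x, however small the true change. Using the same substituted number for flags means that a flag can contradict, or go beyond, what the laboratory reported.

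At stake is the accuracy of the group-by-timepoint safety tables, which compare up to 8 subjects per impairment group with 8 to 24 controls (SAP Section 5), and of the out-of-range flags in the listings.

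**Working it through.** The plan states no figure on this point, so there is nothing to reproduce. The inputs from the documents are the two substitution values, the definition of change and the group sizes. All distributions below are assumptions.

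**1. Group mean (no distributional assumption).** Let f be the share of a group recorded as `<x`, with true values t between 0 and x.

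- 0 rule: error = −(sum of censored t)/n, which lies between −f·x and 0.
- x/2 rule: error = (sum of (x/2 − t))/n, which lies between −f·x/2 and +f·x/2.

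For example, with 2 of 8 results below x, f = 0.25. The 0 rule errs by 0 to −0.25x, and the x/2 rule by at most 0.125x either way. If the censored values were uniform on (0, x), the expected error of the 0 rule would be −0.25 × x/2 = −0.125x.

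**2. Change from baseline.** If both values are below x, the recorded change is 0. If baseline is b < x and the later value is v > x, the 0 rule records v instead of v − b, an overstatement of b, which can approach x. Crossing downwards gives the mirror image. With no true shift the two directions cancel on average and only the spread grows.

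**3. Size under assumed distributions.** Simulation of 400,000 subjects: lognormal values, between-subject SD 0.40 and within-subject SD 0.15 on the log scale, no true change. Entries other than the share are in units of x.

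| Median | Share below x | Mean error, 0 rule | Mean error, x/2 | SD of change, true | 0 rule | x/2 |
|---|---|---|---|---|---|---|
| 0.7 | 80% | −0.506 | −0.106 | 0.177 | 0.392 | 0.237 |
| 1 | 50% | −0.366 | −0.117 | 0.253 | 0.506 | 0.335 |
| 1.5 | 17% | −0.138 | −0.053 | 0.380 | 0.521 | 0.424 |
| 3 | 1% | −0.005 | −0.002 | 0.763 | 0.768 | 0.764 |
| 10 | 0% | 0 | 0 | 2.528 | 2.528 | 2.528 |

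At a median of x the SD of change is 0.506/0.253 = 2.0 times its true value under the 0 rule, and 0.335/0.253 = 1.3 times with x/2. In every row the error in mean change is at most 0.001x under either rule.

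**4. Mean change with a true 10% fall (units of x).**

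| Median | True | 0 rule | x/2 |
|---|---|---|---|
| 0.7 | −0.077 | −0.085 | −0.054 |
| 1 | −0.110 | −0.165 | −0.116 |
| 1.5 | −0.164 | −0.216 | −0.181 |

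The x/2 rule is closer in the last two rows. In the first, with 80% of baseline values below x, the 0 rule happens to be closer.

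**5. Flags (values equal to a limit of normal counted as in range).**

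| Recorded | Position of x | Flag from substituted value | What the record supports |
|---|---|---|---|
| `<x` | LLN = 0 | none | not low: correct |
| `<x` | x ≤ LLN | low | certainly low: correct |
| `<x` | 0 < LLN < x | low | low or normal: may be false |
| `<=x` | x = LLN | low | normal if the value equals x: may be false |
| `>x` | x = ULN | none | certainly high: flag lost |

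**The case against.** The strongest reply is that the rule is prespecified and its consequences are small. Safety is a secondary objective, SAP Section 8.6.6 plans no inferential analysis, and the listings keep the recorded result beside any flag, with clinical significance shown. SAP Section 8.5.2 also sets concentrations below quantification to 0 for summaries, so the convention is consistent within the plan. And x/2 is only another convention. All of this stands, and it is why the point is minor. It does not make 0 a good stand-in for an analyte that is normally present in blood.

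A reader might also infer more than the documents support:

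- **That the bias falls mainly on healthy controls.** For bilirubin this is plausible: exclusion criterion 23 keeps control liver tests at or below the ULN, while criterion 37 lets impaired subjects lie outside normal ranges. But these criteria concern limits of normal and say nothing about reporting limits. Nothing shows the pattern for the rest of the chemistry, hematology and coagulation panels.
- **That changes from baseline are biased in general.** With no true shift, mean change is unbiased and only its spread grows.
- **That false low flags will occur.** They need an LLN above 0 and below x (or equal to x for `<=x`), and no such analyte can be identified from the documents.
- **That a percentage error can be attached to this trial.** Any such figure rests on assumed medians, variances and limits. The largest values come from cases where almost every result is below x, and there no single substitution works well.

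**Conclusion.** The point holds as a minor one. Wherever `<x` results occur, the 0 rule lowers the group mean by up to f·x. That bound is algebraic and twice the largest error possible with x/2. The rule also inflates the SD of change when subjects cross x, roughly doubling it in the assumed case with half the results below x. It distorts mean change only when there is a true shift. Flags taken from substituted values can be wrong at both ends, under the conditions tabulated above.

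The size in this trial is unknown. If values lie well above x, as in the rows with medians of 3x and 10x, the effect is negligible or nil. For bilirubin a greater effect in controls is probable, but it is an inference. The primary PK analysis is untouched.

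**What to change.** In SAP Section 8.6.2:

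- **Summaries and changes from baseline:** set `<x` and `<=x` to x/2, keep `>x` and `>=x` at x, and say explicitly that changes from baseline are covered. Footnote the number of substituted values in each cell.
- **Flags:** derive them from the recorded result, not the substituted value. Flag low only if x ≤ LLN for `<x`, or x < LLN for `<=x`. Flag high only if x ≥ ULN for `>x`, or x > ULN for `>=x`.

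The cost is a short rewording of the SAP, a small change to the analysis dataset derivation, and a footnote count. There are two downsides. The x/2 value is itself a convention and is unreliable when almost all values lie below x; the footnoted count lets the reader see this. And a result that cannot be placed on either side of a limit of normal will carry no flag, although it remains visible as recorded in the listing.

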8.6.3. Vital Signs Parameters

All vital signs parameters, with changes from baseline, will be listed; any value outside the clinical reference range will be flagged, and whether the out of range value was deemed clinically significant or not clinically significant will be indicated.

The observed results and change from baseline for all vital signs results will be summarized descriptively by hepatic function group and timepoint.

8.6.4. 12-lead Electrocardiogram Parameters

All 12-lead ECG parameters, with changes from baseline, will be listed; any value outside the clinical reference range will be flagged, and whether the out of range value was deemed clinically significant or not clinically significant will be indicated.

The observed results and change from baseline for all 12-lead ECG parameters will be summarized descriptively by hepatic function group and timepoint. QTcF values that are > 450 msec and increase from baseline > 30 msec will be flagged in the data listing.

8.6.5. Other Assessments

Medical history and physical examination will be listed. Any physical examination abnormalities reported will also be flagged as clinically significant or not clinically significant as indicated.

All other safety and tolerability assessments not detailed in the above sections will be listed only.

8.6.6. Safety and Tolerability Statistical Methodology

No inferential statistical analyses are planned.

9. INTERIM ANALYSES

Interim reviews of safety data will be conducted after the first 2 subjects from Group 2 (mild hepatic impairment subjects) and Group 3 (moderate hepatic impairment subjects) and matched-control healthy subjects are enrolled and have completed all study-related assessments including the follow-up phone call. The safety data will include AEs and SAEs, vital signs, physical examinations, ECGs, and clinical laboratory evaluations. Enrollment and dosing for remaining subjects in any group may occur after the interim data for that group are reviewed and the Covance Medical Monitor, Investigator (or designee), and Sponsor agree it is safe to proceed with dosing.

Each interim review will be a teleconference between the Covance Medical Monitor, Investigator (or designee), and/or Sponsor to discuss safety data.

If available, PK data and matched-control healthy subject data may also be used during the interim review.

10. SIGNIFICANT CHANGES FROM THE PROTOCOL-SPECIFIED ANALYSES

There were no significant changes from the protocol-specified analyses.

